2.1.3.1. Alternate hypothesis

- The incidence of vascular changes (exudates, hemorrhages, areas of capillary closure) will be less than 50% of the cases, regardless of pathogen or treatment indicated.

3. Study design

According to the moment at which the information is collected.

- Prospective - a study where the information will be collected in the future, after the beginning of the research

3.1. According to the number of times the primary variable of interest is measured or determined.

- Longitudinal.- The primary variable of interest is measured more than once over time

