3.3. According to the analysis of the study population(S)

- Descriptive.- The researcher only has a population and describes it

4. Methodology

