4.1. Place and duration

The population will be patients of the retina and vitreous service of Asociación para Evitar la Ceguera en México, attended from July to December 2024, who have a complete clinical record (age, sex, pathological personal history, non-pathological personal history, heredofamilial history, ophthalmologic history, allergies, medications, ophthalmologic examination with visual acuity, intraocular pressure at each visit), signed informed consent and with a history of exogenous or endogenous endophthalmitis with clear resolution criteria and clear means one week and one month after meeting the resolution criteria to be able to perform fluorescein angiography at both visits.

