4.2 Description

Patients who meet the inclusion criteria will be invited to participate in the study, who will have a history of endophthalmitis and who have clear media (clear cornea, anterior chamber cellularity + or less, vitritis + or less), one week and one month after meeting the resolution criteria established by the Mexican Endophthalmitis Group.

After signing the informed consent form

A comprehensive ophthalmologic examination will be performed, including assessment of visual acuity and intraocular pressure.

A fluorescein angiography will be performed one week after meeting resolution criteria, and one month later.

Fluorescein 10% (10mg/ml) will be injected intravenously through a peripheral line.

Fundus photographs will be taken with the Clarus 700 equipment

The pictures will be analyzed in different phases and in different areas

The changes will be compared at different times, one week after meeting the resolution criteria and one month later

Consecutive recruitment will be done

Protocol ID: CVAE 01

The data will be stored in a table in Excel 2007

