4.3. Exclusion criteria

- Patients who have not signed the informed consent
- Patients under 18 years.
- Patients with endophthalmitis who do not meet the resolution criteria of the Mexican Endophthalmitis Study Group

Protocol ID: CVAE 01

5. Study variables

Variable name	Independent or Dependent	Nominal /ordinal/ dimensional	Unit of measurement	Measurement instrument	Time of measurement
Visual acuity	Independent	Ordinal	logMAR	Snellen Chart	At diagnosis, one week after resolution, and one month after
Vascular changes in FAG (Areas of capillary closure)	Independent	Ordinal	Disc areas	Fluorescein angiography	one week after resolution and one month after
Vascular changes in FAG (Periphlebitis)	Independent	Ordinal	Presence or absence	Fluorescein angiography with fluorescein	one week after resolution and one month after
Vascular changes in FAG (Hejorrhages on staining)	Independent	Ordinal	Presence or absence	Fluorescein angiography with fluorescein	one week after resolution and one month after
Vascular changes in FAG (Areas of leakage)	Independent	Ordinal	Disc areas	Fluorescein angiography	one week after resolution and one month after

Isolated body	Independent	Ordinal	Presence or absence of microorgan	Medium Culture	Single. When an organism grows in the culture
---------------	-------------	---------	-----------------------------------	----------------	---

Protocol ID: CVAE 01

			ism in culture		
--	--	--	----------------	--	--

Age	Independent	Dimensional	Years completed	Interrogation	Visit 1
-----	-------------	-------------	-----------------	---------------	---------

Sex	Independent	Nominal, dichotomic	Female/ Male	Tab from the collection	Unique
-----	-------------	---------------------	--------------	-------------------------	--------

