The structures to be evaluated include the **optic nerve, retina, retinal vasculature**, and transparency of the **posterior segment media**, among others. This procedure will be performed **at all study visits** by the designated clinical team.

Spectral-Domain Optical Coherence Tomography (SD-OCT)

OCT imaging will be performed using the HRA Spectralis Heidelberg, Serial # Spec-CAM-15095-S3610, with a Magnification of 30° and Software version 7.0.6.0. This will aid in evaluating the retinal condition, including central macular thickness and central retinal volume (commonly referred to as macular cube volume in OCT terminology).

A technician or delegated personnel may carry out this procedure, and will be performed at all study visits.

Fundus Photography and Fluorescein Angiography

Fundus imaging will be performed using the **Clarus 700 Zeiss**, Serial #CL700-73467, Software version 1.1.2.59261, Digital Camera Magnification 133°. Images of the **posterior pole and retinal periphery** will be captured, providing a comprehensive view of retinal integrity, the optic nerve, and its vasculature.

Fluorescein angiography will be performed subsequently to evaluate **associated vascular changes**. The patient must undergo an **8-hour fast** and have **pupillary dilation with TP Ofteno® (tropicamide 5% / phenylephrine 0.8%)**. The procedure involves preparing the patient with aseptic technique for an **intravenous injection of fluorescein dye** in an upper limb, followed by imaging with a fundus camera.

It is not essential to use a device of a specific brand or model, as long as a system with **equivalent specifications** is used consistently for the **same patient throughout the study**. The procedure may be performed by a **technician or**

Protocol ID: CVAE 01

delegated personnel, and will be conducted **at all study visits** (7 days and 1 month after meeting the inactivation criteria for endophthalmitis).

Sample size

A review of hospital medical records was conducted to identify patients diagnosed with **endophthalmitis** from **February 2024 to September 2024**, resulting in a total of **57 patients**.

Considering this data was collected over 8 months, a **proportional extrapolation** was made to estimate the number of cases in a **12-month calendar year**, yielding approximately **86 patients**.

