Based on this projection, we decided to use the **sample size formula for proportion estimation**, as our working hypothesis suggests that the **incidence of vascular changes** will be **greater than 50%**.

The sample size was calculated using an **online proportion estimation calculator**:

<https://www.calculator.net/sample-size-calculator.html?type=1&cl=95&ci=5&pp=50&ps=86&x=Calculate>:

Result

Sample size: **71**

This means 71 or more measurements/surveys are needed to have a confidence level of 95% that the real value is within $\pm 5\%$ of the measured/surveyed value.

Confidence Level:	95%	
Margin of Error:	5 %	
Population Proportion:	50 %	Use 50% if not sure
Population Size:	86	Leave blank if unlimited population size.

Calculate  **Clear**

A total of **71 patients** were included to achieve a **95% confidence interval**, with a **5% margin of error**, a **population proportion of 50%**, and a **total population size of 86 patients**.

We will calculate **measures of central tendency** (mean, median, and mode). **Chi-square tests** will be used for qualitative variables.

Data will be analyzed using the **SPSS software, version 25**.

Organization

Human Resources:

- Retina specialists affiliated with the Retina Service
- Medical intern completing social service
- Retina fellows
- Nursing staff

Protocol ID: CVAE 01

Material Resources:

- Computer
- **HRA Spectralis Heidelberg OCT**, Serial #Spec-CAM-15095-S3610, Magnification 30°, Software version 7.0.6.0
- **Clarus 700 Zeiss**, Serial #CL700-73467, Software version 1.1.2.59261, Digital Camera Magnification 133°
- Dye
- Needles
- Plastic catheters
- Vials of fluorescein

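### The only test named for qualitative variables, chi-square, does not in its ordinary form suit the week-1 versus month-1 comparison of present/absent findings in the same patients

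*Protocol*

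**What the plan says.** The analysis text closes Section 5.2 of the protocol. Beyond measures of central tendency it has one sentence on testing: "Chi-square tests will be used for qualitative variables". It makes no exception, and the protocol names no other test.

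Section 4.2 (Description) states the comparison over time: "The changes will be compared at different times, one week after meeting the resolution criteria and one month later". Section 4.1 requires clear media at both time points "to be able to perform fluorescein angiography at both visits", so each patient supplies two readings. Section 3.1 calls the design longitudinal ("The primary variable of interest is measured more than once over time"), and Section 3.3 says there is one group only ("The researcher only has a population and describes it").

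The variables table in Section 5 lists four angiographic variables, each read at both visits. Periphlebitis and hemorrhages are recorded as present or absent. Capillary closure and leakage are measured in disc areas.

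**The concern.** For periphlebitis and hemorrhages, the visit comparison is a paired comparison of two proportions. An ordinary chi-square test can be applied to such data in two ways, and neither answers the question.

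- **Stacked table (visit by finding).** The 71 patients appear twice and are treated as 142 independent readings. If a patient's two readings are positively correlated, the test is conservative and can miss real resolution or progression.
- **Cross-table (week-1 reading by month-1 reading).** The test asks whether the two readings are associated. Readings of one patient usually are, so the test is often significant when the rate has not moved. A reader could take that p-value as evidence of change.

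**Working it through.** **Inputs from the protocol.** n = 71 patients (Section 5.2), two readings each (Sections 4.1 and 5), binary outcome. The 71 reproduces: 57/8 × 12 = 85.5, taken as 86; n0 = 1.96² × 0.25/0.05² = 384.15; 384.15/(1 + 384.15/86) = 70.27, rounded up to 71. It is used here only as the number of pairs.

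**Assumptions, not in the protocol.** All 71 pairs are complete. The rates p1 (week 1) and p2 (month 1), and the within-patient correlation ρ, are varied over a range.

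**Paired cell probabilities.** P(present at both) = p1p2 + ρ√(p1q1p2q2), with q = 1 − p. For 60% to 45% at ρ = 0.5: 0.27 + 0.5 × √0.0594 = 0.392. Resolved is then 0.60 − 0.392 = 0.208, new is 0.45 − 0.392 = 0.058, and absent at both is 0.342.

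**Why stacking is conservative.** The variance of the difference is [p1q1 + p2q2 − 2ρ√(p1q1p2q2)]/n, and the stacked test leaves out the last term. For 60% to 45%, the 95% half-width that ignores pairing is 1.96 × √(0.4875/71) = 0.162. The paired half-width is 0.162, 0.136 and 0.115 at ρ = 0, 0.3 and 0.5.

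**Power, 60% to 45%** (all paired 2×2 tables with n = 71 enumerated, two-sided 0.05, Pearson without continuity correction):

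| ρ | Stacked chi-square | Exact McNemar | Mid-p McNemar |
|---|---|---|---|
| 0 | 0.444 | 0.363 | 0.420 |
| 0.2 | 0.437 | 0.430 | 0.493 |
| 0.3 | 0.432 | 0.481 | 0.548 |
| 0.5 | 0.417 | 0.641 | 0.711 |

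**Other changes, stacked versus exact McNemar:**

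| Change | ρ = 0.3 | ρ = 0.5 |
|---|---|---|
| 60% to 40% | 0.710 vs 0.752 | 0.743 vs 0.900 |
| 60% to 30% | 0.981 vs 0.988 | 0.994 vs 1.000 |
| 60% to 55% | 0.055 vs 0.073 | 0.029 vs 0.090 |

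**Rejection rate with no change (50% at both visits):**

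| ρ | Stacked | Cross-table | Exact McNemar |
|---|---|---|---|
| 0 | 0.053 | 0.054 | 0.033 |
| 0.2 | 0.031 | 0.402 | 0.030 |
| 0.3 | 0.021 | 0.732 | 0.030 |
| 0.5 | 0.006 | 0.994 | 0.029 |

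With a real fall from 60% to 45%, the cross-table test is significant 0.733 and 0.995 of the time at ρ = 0.3 and 0.5. These are almost the same rates as with no change, so its result says nothing about change.

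**Example without change.** Present at both 24, resolved 12, new 12, absent at both 23, so 36/71 at each visit. Cross-table: χ² = 71 × (24 × 23 − 12 × 12)²/(36 × 35 × 36 × 35) = 7.44, p = 0.006. Exact McNemar (12 against 12): p = 1.00.

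**Example with change.** 43/71 at week 1 and 32/71 at month 1. The stacked test gives p = 0.064 whatever the pairing. Exact McNemar gives p = 0.019 with 15 resolved and 4 new, 0.043 with 18 and 7, and 0.090 with 23 and 12.

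**The case against.** The strongest reply is that the link between test and comparison is inferred. Section 5.2 does not mention visits, Section 4.2 names no test, and Section 3.3 calls the study descriptive. If the visits are only to be described, nothing is mis-tested. This stands as a limit on the point.

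Chi-square also has proper uses here, such as comparing patients by pathological history, sex or culture result with one record each. That is right, and those uses should stay.

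McNemar's large-sample test is itself a chi-square test, so the plural could be read to include it, and a separate analysis plan may say so. Both are possible. But the protocol assigns a test to every qualitative variable without mentioning pairing, so the point concerns what it states, not detail left for later.

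The harm is also conditional. Stacking adds no false positives when the correlation is positive, and at low correlation it loses nothing against exact McNemar. The high cross-table rejection rates are not errors of that test, which correctly detects association. Harm requires that someone builds this table and misreads it. All of this stands and keeps the point minor.

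Finally, Section 5 labels the disc-area variables ordinal, as it does the binary ones. They are measured as areas, so this point does not cover them, although the label leaves their handling unclear.

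**Conclusion.** The concern holds, as a minor one. In its ordinary sense, the one test named for qualitative variables does not fit the one comparison over time that the methods describe, for the two present/absent angiographic findings.

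The size depends on the form used and on assumed rates and correlations. Stacking costs material power only for mid-sized changes with correlation well above 0.2. The cross-table form is uninformative about change at any correlation, and at 0.2 it is already significant 40% of the time when nothing has changed.

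The 50% incidence hypotheses and the sample size of 71 do not depend on this comparison. If it is meant as description only, what remains is a clarification of wording.

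**What to change.** Add to the analysis text in Section 5.2 that week-1 versus month-1 readings of periphlebitis and hemorrhages are compared with McNemar's test, exact or mid-p when discordant pairs are few. Report the numbers resolved and new, with a 95% confidence interval for the paired difference in proportions. If no test of change is intended, say so and report the paired counts and the interval only. Keep chi-square, or Fisher's exact test where counts are small, for comparisons between different patients.

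The cost is one or two sentences. No new data are needed: both readings per patient are already planned, and everything follows from the four paired counts.

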5.3. Ethical Aspects

This study was designed in accordance with the principles of the Declaration of Helsinki and in compliance with the guidelines for good clinical practice. All patients must sign an informed consent form prior to their inclusion in the study. Patient privacy will be protected at all costs, and only data relevant to this research will be collected.

